Pain reported during/following PDT will be assessed using an 11-point numeric rating pain scale (NRPS) assessment by the subject (see [Appendix C](#)). The assessed pain should be additionally documented in the eCRF. Further, the NRPS result indicated by the subject should be transformed for documentation in the AE eCRF page as follows: pain 1-3 = mild, 4-7 = moderate, 8-10 = severe.

If possible, each subject should be assessed by the same investigator(s)/staff personnel at each visit.

At each visit or during the phone contact(s) after the PDT sessions, subjects will also be asked if they have experienced any adverse reaction since their previous clinic visit using questions like "Have you noticed anything in the study surrounding areas since we last saw you?" Any signs or symptoms reported by the subject that correspond to one of the 10 local skin reaction categories and/or 3 local discomfort categories listed above should be scored for severity according to the subject's response to the following question: "How much, if any, difficulty or disruption has this (sign) caused you?"

Using the information provided by the subject, the clinical staff should record the most severe reaction reported by the subject in each category with start and stop date (if applicable) using the descriptors listed below:

- 0 = none (no reaction recalled by the subject)
- 1 = mild (the subject is aware of the signs and symptoms, but the signs and symptoms are well tolerated and do not interfere with daily activities)
- 2 = moderate (the signs and symptoms are sufficient to restrict, but not to prevent, usual daily activities for the subject)
- 3 = severe (the subject is unable to perform usual daily activities).

New lesions

Assessment of new lesions during the clinical observation period and the FU part of the study will include new NMSC and melanoma, as well as new AK lesions.

New lesions with indication of localization(s) and reference to the treatment field(s) should be reported as (S)AE. These new lesions may be treated during the clinical observation period with

physical measures at the discretion of the investigator and without restriction during the follow-up period. Please refer to [Section 6.2 Concomitant treatments for restrictions](#).

Physical examination

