8.1.2 Serious adverse event

Any adverse event should be assigned to be unrelated or related to either the study medication, the medical device (BF-RhodoLED®, or both, as this will be important for evaluation of the safety of BF-200 ALA or the lamp.

In general, an **SAE** is one that occurs at any dose (including overdose) and

- Results in death.
- Is life-threatening.

“Life-threatening” means that the subject was at immediate risk of death at the time of the SAE; it does not refer to an SAE that hypothetically might have caused death if it were more severe.

- Requires inpatient hospitalization or prolongation of existing hospitalization.

This means that hospital inpatient admission or prolongation of hospital stay were required for the treatment of the AE, or that they occurred as a consequence of the event.

- Results in persistent or significant disability or incapacity.

“Persistent or significant disability or incapacity” means a permanent or significant and substantial disruption of a person’s ability to carry out normal life functions”.

- Is a congenital anomaly or birth defect.
- Is an important medical event.

Medical and scientific judgment should be exercised in deciding whether expedited reporting is appropriate in situations where none of the outcomes listed above occurred.

Important medical events that may not be immediately life-threatening or result in death or hospitalization but may jeopardize the subject or may require interventions to prevent one of the other outcomes listed in the definition above should also usually be considered serious. Examples of such events include allergic bronchospasm requiring intensive treatment in an emergency room or at home, blood dyscrasias, or convulsions that do not result in inpatient hospitalization, or the development of drug dependency or drug abuse.

A diagnosis of a second cancer during the course of a treatment should be considered as medically important.

The term “severe” is often used to describe the intensity (severity) of a specific event (as in mild, moderate, or severe myocardial infarction); the event itself, however, may be of relatively minor medical significance (such as severe headache). This is not the same as “serious”, which is based on the outcome or action criteria usually associated with events that pose a threat to life or functioning. Seriousness (not severity) serves as a guide for defining regulatory reporting obligations.

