11.3.5 Analyses of follow-up data

The follow-up period is performed as a separate part of the study. Data from the follow-up visits will be analyzed and reported separately. In case any data assigned to the observation part of the study should be documented during the follow-up period (e.g. an adverse event will be reported during follow-up phase with start of onset during observation period), those data will be separately listed but not used for descriptive analysis of follow-up data. The analysis variables of the follow-up period are presented in [Section 11.1.3](#).

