## 4 Statistical Evaluation

Missing values of the primary endpoint will be regarded as non-responders. Missing values of clinical lesion assessments only will be imputed using a last observation carried forward (LOCF) approach. If no preceding assessment is available, the lesion will be regarded as non-responding. Further details of handling of missing data are described in section 4.6.

Unless otherwise stated, continuous data will be summarized by means of descriptive statistics, i.e. mean value, standard deviation (SD), first quartile, median, third quartile, range (minimum and maximum), and number of non-missing values. Categorical variables will be summarized by absolute and relative frequencies (percentages on non-missing values) of subjects by category.

Only data belonging to the clinical observation phase will be used for the analysis described in this SAP. For this, data of follow-up visits will be excluded from SDTM data sets used for analysis of clinical observation phase. For visit-scheduled datasets (incl. medical history), all records prior to or at Visit 8 (12 weeks post-PDT-3) - end of clinical study phase - will be included. Subjects with premature termination after Visit 8 will be removed from dataset "Study Termination" (i.e. they will not be identified as drop-outs). Furthermore, adverse events (AEs) and concomitant medications (CMs) starting after date of last visit/assessment of clinical phase (maximum date of all visit/assessment dates within non-log forms prior to or at Visit 8) on subject level will be excluded. If the month and/or day of the start date of AE or CM is not available, a worst-case-approach will be included when that assumed date is prior or at the maximum date of all visits and assessments prior to or at Visit 8. If the complete start date is not known, a worst-case-approach will be applied, and a date of 2000-01-01 will be assumed, to ensure that it will be prior to the maximum date of all visits and assessments prior to or at Visit 8.

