#### Frequency and extent of TEAEs, including SAEs

TEAEs are defined as all AEs with time of onset on or after the time of treatment with randomized IMP within 4 weeks (28 days) after each PDT cycle. If time of onset of AEs is not within 4 weeks (28 days) after each PDT cycle, but is identified to be at least possibly related to IMP or medical device, AEs will be assumed as TEAEs. The reference dates will be calculated as date of last PDT within each PDT cycle + 28, i.e. date of PDT-2 and/or PDT-4, respectively. If PDT-2 and/or PDT-4 are not available, the dates of PDT-1 and/or PDT-3 will be used for calculation of reference dates. These reference dates will be used for assignment of TEAEs. If unclear due to incomplete start time/date of AE or PDT, AEs will be assumed as TEAEs, as far as end time/date of AE is not before first treatment in first PDT cycle. AEs and TEAEs will be summarized and tabulated according to primary system organ class and preferred term displaying the number of events as well as counts and percentages on a subject basis per treatment arm.

[figure not shown]
Additionally, TEAEs by sex, TEAEs by age group I, serious TEAEs and TEAEs by intensity (mild/moderate/severe/unknown) will be tabulated. Related TEAEs (defined as possibly, probably, or definitely related, or with missing relationship) will be presented by intensity overall (related to IMP or related to medical device), related to IMP only, related to IMP and medical device and related to medical device only. Additionally, TEAEs by relationship (unrelated / unlikely related / probably related / probably related / definitely related) will be presented related to IMP and related to medical device separately.

TEAEs leading to death and TEAEs resulting in discontinuation of study will be tabulated if more than 5 events are observed. Specification of any action taken documented on AE page as 'Withdrawal from study' will be used for detection of TEAEs resulting in discontinuation of study.

A listing of subjects with TEAEs will be provided for all TEAEs reported. Non-TEAEs, i.e. AEs with onset before treatment or later than 4 weeks after each PDT cycle, will be listed separately for all subjects enrolled. In listings, the start day of the AE relative to start of treatment will be calculated for complete start dates only. Duration of events is only calculated for complete start and end dates.

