#### New lesions (AK, NMSC, melanoma)

The occurrence of any new lesions (AK, NMSC, melanoma, according to AE CRF page) since screening will be summarized and tabulated according to primary system organ class and preferred term displaying the number of events as well as counts and percentages on a subject basis. Additionally, the occurrence of any new lesions will be tabulated stratified by location in relation to the treatment field (outside/inside treatment field).

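### SAP section 4 sorts adverse events by start date alone, so one first reported in follow-up with no start date enters the clinical-phase data and is counted as a TEAE

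*SAP*

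**What the plan says.** SAP section 4 restricts the analysis to the clinical observation phase and states that "data of follow-up visits will be excluded from SDTM data sets used for analysis of clinical observation phase". Records tied to a visit are kept up to Visit 8. Adverse events have their own rule: those "starting after date of last visit/assessment of clinical phase" are dropped for each subject. If no part of the start date is known, the SAP says: "If the complete start date is not known, a worst-case-approach will be applied, and a date of 2000-01-01 will be assumed". Its stated purpose is to place the record before the cut-off. If only the month or day is missing, the event is kept when an assumed date falls on or before the subject's last clinical-phase date. In the copy available that sentence is broken and does not give the assumed date.

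SAP 4.5 sets the TEAE window at 28 days after the last PDT of each cycle, and adds any event at least possibly related to IMP or device. For incomplete dates it says: "If unclear due to incomplete start time/date of AE or PDT, AEs will be assumed as TEAEs". The only exception is an event that ended before the first treatment. The new-lesion table, also in SAP 4.5, covers "The occurrence of any new lesions (AK, NMSC, melanoma, according to AE CRF page) since screening" and has no upper time limit of its own.

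Protocol 7.3.2 says: "Assessment of new lesions during the clinical observation period and the FU part of the study will include new NMSC and melanoma". It asks for new lesions to be reported as adverse events, serious where applicable. Under Protocol 8.2 all adverse events are collected until Visit 5 or Visit 8, and only selected events during the following years.

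**The concern.** The cut-off and the TEAE rule both look at when an event started. Neither looks at when it was first reported. If the start is unknown, the 2000-01-01 convention overrides everything else, including the fact that the event may first have been mentioned years after the last PDT.

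Follow-up records are likely to be in the database. SAP section 4 describes stripping follow-up visits out, and the SAP carries the date 29Jul2024, against a planned end of the clinical phase in about November 2019 (Protocol synopsis). Follow-up visits are 12 to 24 months apart, so some onsets may be recalled poorly.

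At stake is whether the clinical-phase TEAE and new-lesion tables describe only the clinical phase. Collection differs between the phases, so a late event under the wrong heading is not comparable with the others in the table. SAP section 5 already changed the protocol's TEAE definition to avoid misassignment caused by visit windows of about a week. An error of months or years is the same kind of error, but larger.

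**Working it through.** The plan gives no figure to reproduce. The check traces the rules for an event whose true onset lies in follow-up and which is not considered related to IMP or device.

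**Inputs.** PDT-2 is 7 to 14 days after PDT-1. Visit 5 is 77 to 91 days after PDT-1 (12 ± 1 weeks), and Visit 8 is the same distance after PDT-3. The TEAE window closes 28 days after the last PDT of the cycle. Follow-up runs to 60 months after Visit 5. Planned arms are 149 and 37.

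**Assumptions of mine.** Partial dates are set to the earliest possible day. Onset is uniform over follow-up. Last clinical visits are spread evenly over the calendar year.

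**Start wholly unknown.** The assumed date, 2000-01-01, is before any cut-off, so the event is always kept. Onset is unclear, so it is a TEAE unless its end precedes first treatment, which a follow-up event cannot satisfy. Result: 100% enter and 100% are TEAEs.

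**Year only.** The assumed date is 1 January, so the event enters only if its year is the one in which the clinical phase ended. With the last visit at fraction u of the year and onset uniform over the next T years, the chance is (1 − u)/T, which averages 1/(2T):
- T = 1: 50%
- T = 2: 25%
- T = 5: 10%

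To become a TEAE, the year must also overlap a TEAE window. The window closes on day 35 to 42 (7 to 14 plus 28), about 45 days before a visit at day 84. The share is (1 − 45/365)²/(2T):
- T = 1: 0.877²/2 = 38%
- T = 2: 19%
- T = 5: 7.7%

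If the SAP instead assumed the latest possible day, these year-only shares would be 0%.

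**Day missing, month known.** The month containing Visit 5 starts no earlier than day 77 − 30 = 47, after the window has closed (day 42 at the latest). The same holds for Visit 8 counted from PDT-3. Such an event can enter if it falls in the month of the last visit, but it cannot be a TEAE unless at least possibly related.

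**Simulation.** 100,000 events per scenario, onset uniform to 60 months after Visit 5, PDT-1 dates spread over four years from October 2018:

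| Start date known | Enters clinical data (one / two cycles) | Counted as TEAE (one / two cycles) |
|---|---|---|
| Nothing | 100% / 100% | 100% / 100% |
| Year only | 9.9% / 10.5% | 7.6% / 8.0% |
| Month and year | 0.8% / 0.9% | 0% / 0% |
| Complete | 0% / 0% | 0% / 0% |

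**Effect of one subject.** Vehicle 1/37 = 2.7 points; active 1/149 = 0.7 points.

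**The case against.** The strongest reply is that SAP section 4 opens by limiting the analysis to clinical-phase data, with the start-date rule as a further exclusion. The intention is clear. But adverse events are log records, and the section gives them a rule based only on start date. Followed literally, that rule keeps the undated event.

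Second, missing dates should be rare. Protocol 8.3.1 asks for start and stop dates, Protocol 14.1 for an explanation of missing data, and SAP 4.8 for all queries to be resolved before closure. This stands as an argument about frequency, not about the rule.

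Third, counting uncertain onsets as TEAEs is deliberately conservative, safety is descriptive, and TEAEs are listed. This limits the consequence. However, relative start day is calculated only for complete dates, so nothing specified for the listing shows that a record came from follow-up.

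A reader might infer more than the documents support:
- That any incomplete start date causes the problem. Section 4 screens out most partial dates, as the table shows.
- That the affected events are mainly new skin cancers. Recurrences, local events and relevant SAEs are also collected in follow-up, and no frequencies are given.
- That new cancers would swell the serious-TEAE table. Protocol 8.1.2 says: "A diagnosis of a second cancer during the course of a treatment should be considered as medically important". That wording concerns the course of treatment and does not settle how a cancer found years later is classified.
- That the follow-up report loses the same events. Protocol 11.3.5 says of observation-phase data documented late that "those data will be separately listed but not used for descriptive analysis of follow-up data". Its example is an event with onset in the observation period, it does not mention assumed dates, and the follow-up analysis has its own SAP, which is not available here.

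**Conclusion.** The concern holds for adverse events first reported in follow-up with a wholly unknown start: every such record enters the clinical-phase data and is counted as a TEAE, and a new lesion also enters the new-lesion table. It holds in part for year-only starts in the calendar year the clinical phase ended: about 10% enter and about 8% become TEAEs over 60 months, or about 50% and 38% if onset is confined to the first 12 months. The year-only figures depend on assuming the earliest possible day. Dates missing only the day enter in under 1% of cases.

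The number of affected records cannot be derived from the documents and may be small. The primary analysis is unaffected. The point deserves correction because the stated rule contradicts the restriction that the same SAP section sets, and because one misplaced subject is visible in a vehicle arm of 37.

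**What to change.** In SAP sections 4 and 4.5, apply the worst-case rules for wholly unknown or year-only start dates only to adverse events first reported at or before the subject's last clinical-phase visit (Visit 5 or Visit 8). Decide this by the visit or report date. Use the eCRF entry date only as a fallback, because entry can lag the visit. Assign such events first reported at a follow-up visit to follow-up and list them separately.

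Leave two things as they are. Events at least possibly related to IMP or device continue to count as TEAEs under SAP 4.5. Late-reported events whose known month or year places onset in the clinical phase stay there.

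State the assumed date in the partial-date sentence of SAP section 4, or confirm that the full document already does.

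The cost is one derivation rule and one listing. The downside is small: a true clinical-phase event first mentioned in follow-up with no usable date would be counted in follow-up, but the listing keeps it visible.

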Non-responders or partial responders according to clinical assessment after the 1st PDT cycle, i.e., subjects with visible remaining target lesions at Visit 5 (Week 12 after PDT-1), will have the clinically remaining lesions retreated with a 2nd PDT cycle starting at Visit 5 (PDT-3). If the Main Target Lesion is clinically cleared at this time point, it will be excised at this Visit 5. PDT-4 will be applied 1-2 weeks later, at Visit 6. Subjects will then be contacted by phone 1 week ± 2 days after the 2nd PDT cycle ended, and attend two further visits for assessment of efficacy and safety (Visit 7: 5 weeks ± 1 week after PDT-3, and Visit 8: 12 weeks ± 1 week after PDT-3). At Visit 8, a final clinical assessment will be performed identifying complete clinical responders 12 weeks after the start of the 2nd PDT cycle and partial or non-responders, i.e., subjects still showing remaining target lesions after the 2nd PDT cycle. A retreated Main Target Lesion will be excised on this day, irrespective of the clinical outcome.

In general, clinically complete responders are categorized 12 weeks after the start of the last PDT cycle (PDT-1 or PDT-3) according to clinical assessment only and are defined as subjects with all Target Lesions (Main plus Additional Target Lesions) clinically cleared.

All subjects will receive excision of their Main Target Lesion, at the latest at Visit 8 for histopathological evaluation of lesion status. Along with the excision of the area of the Main Target BCC Lesion, the ink marks applied at Visit 2 will be removed. Any remaining Additional Target Lesions at Visit 8 will be treated at the discretion of the investigator following completion of final assessments of the clinical observation period.

For all subjects who completed the clinical observation period, four FU visits are scheduled (12 ± 1 months, 24 ± 2 months, 36 ± 2 months and 60 ± 2 months after completion of PDT cycle 1 (Visit 5)). All subject data listed in [Section 7.1](#) and results of assessments have to be recorded in the subject electronic case report form (eCRF). Data reported during the FU part of the study will be analyzed and reported separately and are not part of the clinical observation period of the study.

Inclusion and exclusion criteria

Main inclusion criteria:

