3.2 STUDY DURATION, DATES, AND END-OF-STUDY DEFINITION

The last subject last visit of the study is expected to be approximately in August 2024.

A recruitment period of approximately 9 months will be followed by a clinical observation period of either 12 or 24 weeks. This is determined by the response status of the subject at Visit 5, 12 weeks after PDT-1. After this period, i.e. 12 weeks after the start of the last PDT cycle, the clinical observation part of the study will be completed (last subject out of the clinical phase approximately in November 2019). The clinical observation part is followed by a FU part that includes 4 additional visits (i.e., 12, 24, 36 as well as 60 months after completion of the 1st PDT cycle (Visit 5)) and will be completed for the last subject approximately in August 2024. The actual duration of the subject recruitment period and consequently the whole study may vary.

The end of the study is defined as the date of database lock, approx. 2 month after the last follow-up visit of the last subject (approx. in October 2024).

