8.2 PERIOD OF OBSERVATION

For the purposes of this study, the period of observation for collection of AEs extends from the time the subject gives informed consent until the end of the clinical observation period of the study at Visit 5 or Visit 8 (in case of re-treatment with a 2nd PDT cycle).

At the FU visits, any local AEs (i.e., AEs affecting skin health in the treatment fields), which might impair proper assessment of the recurrence of the treated sBCC lesions, or other clinically relevant

events at the investigator's discretion, or conditions that may be relevant for proper assessment of the recurrence of the treated BCC lesions) should be documented including any recurrent BCC lesions and any new lesions (AK, other NMSC, and melanoma) (see [Section 7.2.3](#)).

Relevant SAEs or related SAEs (SARs) should be documented until the end of the FU period (60 months after completion of the 1st PDT cycle (Visit 5)).

If the investigators detect an SAE in a subject after the end of the FU period, and considers the event possibly related to prior study treatment or procedures, they should report this event to the pharmacovigilance department of the sponsor.

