11.3.1 Disposition of subjects and exposure

The number and relative frequencies of subjects in each analysis set such as the enrolled set, the randomized set, the SAF set, the FAS, and the PPS will be presented overall, and by treatment, site, and study part (clinical observation period or FU).

The number and relative frequency of subjects who prematurely discontinued the study and the number of subjects completing the study parts will be presented. Reasons for discontinuation will be tabulated by treatment group.

The number and relative frequency of subjects treated and re-treated with PDT will be presented by treatment group.

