#### Local reactions in the treatment field(s)

Local reactions, i.e. local skin reactions and local discomfort as assessed by investigator, are documented on AE page and can be identified as AEs with CRF question 'Is this (S)AE within a treatment field?' answered with 'yes' and are related (defined as possibly, probably, or definitely related, or with missing relationship) to IMP or medical device. Variable will be 'yes' if local reaction is documented at least once. Otherwise, variable will be 'no'. TEAEs identified as local reaction will be tabulated separately by intensity (mild/moderate/severe/unknown) separately for each PDT cycle. Therefore, local reactions with time of onset on or after the time of PDT-1 and before the time of PDT-3 will be categorized to PDT cycle 1. Local reactions with time of onset on or after the time of PDT-3 will be categorized to PDT cycle 2. If PDT-1 and/or PDT-3 are not available, the dates of PDT-2 and/or PDT-4 will be used for calculation respectively. If unclear due to incomplete start time/date of local reactions or PDT, local reactions will be categorized to PDT cycle unknown. Furthermore, the worst intensity (none/mild/moderate/severe) of at least one occurred PTs will be presented for local reactions. Thereby not available local reaction will be presented as intensity none. Missing or unknown intensity will not be considered for worst intensity analysis. Additionally, the frequency of any TEAEs identified as local reaction will be presented together with the respective CIs for each treatment group.

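### SAP 4.5 pools the main TEAE tables over one or two response-dependent PDT cycles; adding cycle-1 versions would allow comparison at equal planned exposure

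*SAP*

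**What the plan says.** **Who gets a second cycle.** Under the protocol synopsis (Study design) and section 5.1.2, only subjects with a target lesion still clinically visible at Visit 5 are retreated. Protocol 3.2 accordingly sets a "clinical observation period of either 12 or 24 weeks. This is determined by the response status of the subject at Visit 5". Under protocol 8.2, adverse events are collected from consent "until the end of the clinical observation period of the study at Visit 5 or Visit 8".

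**What counts as a TEAE.** SAP 4.5 counts onset from treatment to 28 days after the last PDT of each cycle. It also counts later events that are at least possibly related to the drug or the lamp. On incomplete dates it says: "If unclear due to incomplete start time/date of AE or PDT, AEs will be assumed as TEAEs", unless the event ended before first treatment.

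**Which tables are pooled as described.** The TEAE table by organ class and preferred term shows event numbers and "counts and percentages on a subject basis per treatment arm". The serious, by-intensity and related TEAE tables follow with no mention of cycle. New lesions are tabulated from screening onward. The frequency of any local reaction, with confidence intervals, is given per treatment group.

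**Which are not.** Local reactions by intensity are tabulated separately per cycle: those "with time of onset on or after the time of PDT-1 and before the time of PDT-3 will be categorized to PDT cycle 1". Discomfort and mean pain are presented by assessment time point.

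**What helps a reader adjust.** Protocol 11.3.1 says: "The number and relative frequency of subjects treated and re-treated with PDT will be presented by treatment group". On listings, SAP 4.5 says: "In listings, the start day of the AE relative to start of treatment will be calculated for complete start dates only".

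**The concern.** The number of cycles is itself an outcome of treatment. A drug that clears lesions leaves fewer of its subjects with a second cycle, a second 28-day TEAE window and a second 12 weeks of observation. A subject-level percentage asks whether a subject ever had an event, so the arm with more cycles has more chances to score. Here that arm is expected to be vehicle, so the comparator percentage rises for a reason unrelated to safety per treatment.

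Readers of a label-extension trial will compare these percentages between arms. The risk is that a relative excess on drug looks smaller than it is per cycle, or that a background event with equal risk per cycle looks less frequent on drug. This matters mainly for non-local, serious and overall TEAEs and for new lesions, because the tables described for these have no cycle split.

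**Working it through.** **Inputs.** The documents give no TEAE rates and no retreatment shares by arm, so there is no planned figure to reproduce. The planned numbers are 149 and 37 (protocol 11.6), taken here as the safety set. The planning response rates of 65% and 25% are composite rates after the last cycle. They suggest more retreatment on vehicle but do not give the shares. Everything else below is assumed.

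**Time at risk.** PDT-1 to PDT-2 is 7-14 days. Adding 28 gives 35-42 days per cycle, or 70-84 for two cycles. This applies to events judged unrelated or unlikely related. At least possibly related events count through Visit 5 or Visit 8.

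**Cycles per subject.** Let r be the retreated share, 0.20-0.40 on active and 0.70-0.80 on vehicle. The vehicle-to-active ratio of cycles, (1 + r_V)/(1 + r_A), runs from 1.7/1.4 = 1.21 to 1.8/1.2 = 1.50.

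**Pooled risk.** P = p + r(1 − p)q, where p is the cycle-1 risk and q the cycle-2 risk given no cycle-1 event.

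With q = p, the pooled ratio is (p_A/p_V) × [1 + r_A(1 − p_A)]/[1 + r_V(1 − p_V)]. If p_A > p_V and r_A < r_V, the bracketed quotient is below 1, so the ratio is always reduced. A grid check agreed in all 29,241 combinations. The risk difference, however, rose in 5,234 of them.

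**Main example, 20% against 10%, q = p.**
- Active: 0.20 + 0.2 × 0.8 × 0.20 = 0.232, to 0.20 + 0.4 × 0.8 × 0.20 = 0.264.
- Vehicle: 0.10 + 0.7 × 0.9 × 0.10 = 0.163, to 0.10 + 0.8 × 0.9 × 0.10 = 0.172.
- Ratio: 0.232/0.172 = 1.35 to 0.264/0.163 = 1.62, against 2.0 per cycle.
- Difference: 6.0 to 10.1 points, against 10.

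**Other assumptions.**

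| Assumption | Pooled ratio |
|---|---|
| Wider shares (10-50% and 70-90%), 20% vs 10% | 0.216/0.181 = 1.19 to 0.280/0.163 = 1.72 |
| 20% vs 2% (per-cycle ratio 10) | 0.232/0.0357 = 6.5 to 0.264/0.0337 = 7.8 |
| 10% vs 10% (per-cycle ratio 1) | 0.118/0.172 = 0.69 to 0.136/0.163 = 0.83 |
| 20% vs 10%, q halved in both arms | 0.216/0.136 = 1.59 to 0.232/0.1315 = 1.76 |
| 20% vs 10%, q halved on vehicle only | 0.232/0.136 = 1.71 to 0.264/0.1315 = 2.01 |
| 20% vs 10%, active q = 0.40 | 0.264/0.172 = 1.54 to 0.328/0.163 = 2.01 |

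At 20% against 2%, the difference grows from 18 to 19.6-23.0 points. If cycle 2 adds no first events, nothing changes. Cycle-2 risk could be lower because only remaining lesions are retreated. It could be higher on drug because a cleared Main Target Lesion is excised on the day PDT-3 is given.

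**Against sampling error (main example).** The 95% half-width of the difference is 1.96 × √[A(1 − A)/149 + V(1 − V)/37] = 13.7 to 14.1 points, where A and V are the pooled active and vehicle risks. The standard error of the log ratio is √[(1 − A)/(149A) + (1 − V)/(37V)] = 0.386 to 0.401. The shift, (ln 2 − ln ratio)/SE, is 0.53 to 1.01.

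**The case against.** The strongest reply is that the effects this drug is expected to cause are already handled. Protocol 8.1.3 says nearly all subjects in the earlier trials had local phototoxic reactions, and SAP 4.5 tabulates these by intensity and cycle. A reader might infer that nothing in 4.5 compares the arms at equal planned exposure. That is not so: the cycle-1 local-reaction table does, and discomfort and mean pain are presented by assessment time point. Even the any-local-reaction frequency may be available for cycle 1, because the worst-intensity summary includes a *none* category and the text leaves open whether it is by cycle. This part of the objection stands and narrows the point.

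Pooled tables are also a legitimate summary of the whole treatment strategy, safety is descriptive, and no planned test is affected. That stands too, and makes this an improvement rather than the correction of an error.

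Readers can adjust in part. Event counts divided by cycles given, using the retreated numbers by arm, yield events per cycle. But that is not the share of subjects with an event, and the listings give start day only for complete dates.

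Finally, SAP 4.9 places the detailed table descriptions in Appendix A, which is not in the supplied text. Cycle-1 tables may be specified there, so silence in 4.5 does not prove they are absent.

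**Conclusion.** The point holds in limited form. As described, the overall, serious, related and by-intensity TEAE tables and the new-lesion table mix subjects observed over one cycle with subjects observed over two, and response decides which. If more vehicle than drug subjects are retreated and cycle 2 adds first events at similar risk, the subject percentages understate the drug's risk ratio.

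The size is unknown. The range of 1.35-1.62 for a true 2.0 rests wholly on assumed shares, assumed risks and independence between cycles. Sampling error is larger than the shift, although the shift is systematic under those conditions.

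Two stronger readings are not supported. One is that pooling hides an absolute excess: the risk difference can move either way. The other is that the distortion is certain: it can vanish if cycle-2 risk is low on vehicle or high on drug. Priority is low to moderate.

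**What to change.** In SAP 4.5:

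- Keep the pooled tables, labelled as the summary of the whole treatment strategy.
- Add cycle-1 versions of the overall organ class/preferred term, serious, related and by-intensity TEAE tables, the any-local-reaction frequency, and new lesions up to Visit 5.
- Keep the existing TEAE definition. Define cycle 1 as onset on or after PDT-1 and before PDT-3, the cut already used for local reactions, or up to Visit 5 if there is no PDT-3.
- Put TEAEs with unclear dates in a separate *cycle unknown* row, as is done for local reactions.
- Give any cycle-2 table the subjects treated in cycle 2 as denominator, and label it as response-selected, not a randomised comparison.
- If Appendix A already has these tables, refer to them in 4.5.

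The cost is SAP wording and a few extra descriptive tables from existing data. No new data collection is needed, and no test or sample size changes.
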